### **8.1.2 Exclusion Criteria at screening**

Patients who meet any of the following criteria will be excluded from the study.

1. Patients in a coma
2. Patients under the strong influence of central nervous system depressants such as barbituric acid derivatives
3. Patients receiving treatment with adrenaline, azole antifungals (excluding drugs for external use), or human immunodeficiency virus (HIV) protease inhibitors
4. Patients with a history of or current neuroleptic malignant syndrome, tardive dyskinesia, or water intoxication
5. Patients with Parkinson's disease
6. Patients with active suicidal ideation or those with a suicide attempt history who are considered ineligible for the study by the Investigator
7. Patients with HbA1c (NGSP) of 8.4% or higher
8. Patients with physical exhaustion accompanied by conditions such as dehydration and malnutrition

9. Patients with a history of or complication(s) involving serious cardiovascular, hepatic, renal, organic brain, hematologic, endocrine, convulsive disease or other conditions, and who are considered ineligible for the study by the Investigator
10. Patients with skin injuries, skin diseases or tattoos that preclude the application of the study drug to the back, chest, or abdomen
11. Patients with a history of drug abuse, drug dependency, alcohol abuse, or alcohol dependency within 6 months (180 days) before screening
12. Patients who received any depot preparation (sustained-release formulation) of an antipsychotics within 3 months (90 days) before screening
13. Patients who received clozapine within 4 months (120 days) before screening
14. Patients who are considered resistant to treatment for psychiatric symptoms by the Investigator. Treatment resistance is defined as failure to respond to 3 or more antipsychotics within 1 year (365 days) before screening
15. Patients who previously received blonanserin
16. Patients who received monoamine oxidase (MAO) inhibitors or fluoxetine within 1 month (30 days) before screening
17. Patients who received electroconvulsive therapy within 6 months (180 days) before screening
18. Patients who are pregnant, or are nursing mothers
19. Patients with a history or complication(s) of hypersensitivity to 2 or more drugs (patients with a history or complication(s) of drug-induced allergic reactions such as anaphylaxis, rash, and urticaria)
20. Patients with a history or complication(s) of malignant tumor within 5 years before screening

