2.2 Overall Study Design

This study has two main phases:

1. Double-blind treatment phase: Multicenter, randomized, double-blind, placebo-controlled, parallel-group design
2. Open-label treatment phase: Multicenter, open-label, flexible dose design

The flowchart for this study is given in Figure 1.

Figure 1: Study Flowchart

The study consists of 4 phases: the washout phase, the double-blind treatment phase, the Open-label treatment phase, and the follow-up phase.

In the washout phase, placebo will be applied once daily for 1 week (at least 3 days) in a single-blind manner. After the washout phase, subjects will be randomized to one of three treatments: 40 mg of DSP-5423P, 80 mg of DSP-5423P, and placebo, at 1:1:1 ratio in the Double-blind treatment phase. The study drugs will be applied once daily for 6 weeks. Subjects who completed the double-blind treatment phase can enter the Open-label treatment phase. In the open-label treatment phase, DSP-5423P will be applied as flexible dose (40, 60, or 80 mg) once daily for 28 weeks (outside Japan) or 52 weeks (in Japan).

Subjects who completed the open-label treatment phase or who prematurely discontinued the study drug after entering the double-blind treatment phase will undergo the follow-up assessments in 1 to 2 weeks after the termination of the study drug.

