6.3 Analysis visits, baseline, and post-baseline measures

All data will be organized and analyzed according to the scheduled timing as outlined in Table 4 to Table 6 Schedule of Assessments and according to the visit denoted in the CRFs. Unscheduled visits may be used if scheduled visits are not available, as specified below. The data collected at the discontinuation visit within 7 days from the final application of study drug will be mapped to the next scheduled visit of the actual discontinuation date, as specified below.

Follow to assign analysis visit;

1. Decide post-base line measures,
2. Assign scheduled visit denoted in the CRFs,
3. Assign CRF discontinuation visits,
4. Assign CRF unscheduled visits, when applicable.

A. Double-blind treatment phase

(i) Baseline analysis visit

Defined as the last non-missing data of CRF Screening or CRF Day 1 (Baseline) visit on or before Day 1. Unscheduled visits will not be used.

Statistical Analysis Plan

Version: 2

Study No. D4904020

(ii) Post-baseline data

Defined as the non-missing data on Day 1 through 7 days after the final application of study drug except for Screening and Day 1 (Baseline) visit. Data assessed on Day 1 and captured in the CRF visits of Week 1, discontinuation, and unscheduled visits will be considered as post-baseline data. Data assessed on Day 1 and captured in the CRF visits of Screening and Day 1 (Baseline) will NOT be considered as post-baseline data.

(iii) Post-baseline analysis visit

The post-baseline data will be mapped to post-baseline analysis visits, ie, Week 1, 2, 4, and 6 as follows:

- (1) CRF Week 1, 2, 4, and 6 will be mapped to the corresponding analysis visits, regardless of the actual day of assessment.
- (2) CRF discontinuation visits will be mapped to the earliest missing analysis visit based on the relative day of assessment as follows:

Assessments and tests	Relative Day	Analysis Visit
PANSS, CGI-S, DIEPSS, C-SSRS, Skin irritation assessment, Body weight, Vital signs	Day 1 to 11	Week 1, 2, 4, 6
	Day 12 to 25	Week 2, 4, 6
	Day 26 to 39	Week 4, 6
	Day 40 or later	Week 6
12-lead ECG, Pharmacokinetic	Day 1 to 11	Week 1, 2, 6
	Day 12 to 25	Week 2, 6
	Day 26 or later	Week 6
Laboratory test	Day 1 to 25	Week 2, 6
	Day 26 or later	Week 6

Note: non-missing analysis visits will not be replaced.

- (3) CRF unscheduled visits will be mapped to the earliest missing analysis visit based on the relative day of assessment as follows:

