* Subjects who have “Y” at baseline will be excluded from denominator in calculation of percentage.

** Regarding “Suicidal Ideation”, in case that “Non-Specific Active Suicidal Thoughts” is “No”, and following 3 items, “Active Suicidal Ideation with Any Methods (Not Plan) without Intent to Act”, “Active Suicidal Ideation with Some Intent to Act, without Specific Plan”, “Active Suicidal Ideation with Specific Plan and Intent” are all null, all of these 3 items will be set to “No”. This is based on a logic which these 3 items supposed to be followed only by a case of “Yes” in “Non-Specific Active Suicidal Thoughts”.

The number and percentage of subjects with suicidal ideation and suicidal behavior

will be summarized by treatment group for all regions and by country for the double-blind treatment phase on the safety population and for the DSP-5423P treatment period on the DSP-5423P dosed population.

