7.7.5 Laboratory Evaluations

Data for the following hematology, blood chemistry, and urinalysis parameters received from the central laboratory will be listed and summarized by treatment group and visit including LOCF endpoints for the double-blind treatment phase using the safety population and for the DSP-5423P treatment period on the DSP-5423P dosed population. Observed values and changes from baseline will be summarized.

Statistical Analysis Plan

Version: 2

Study No. D4904020

Hematology	Blood Chemistry	Urinalysis
1. white blood cell count,	1. total protein,	1. glucose,
2. red blood cell count,	2. total bilirubin,	2. protein,
3. hemoglobin,	3. AST,	3. occult blood,
4. hematocrit,	4. ALT,	4. urobilinogen
5. platelet count,	5. ALP,	
6. neutrophils,	6. γ -GTP,	
7. eosinophils,	7. LDH,	
8. basophils,	8. total cholesterol,	
9. monocytes,	9. triglycerides,	
10. lymphocytes	10. BUN,	
	11. creatinine,	
	12. CK,	
	13. Na,	
	14. K,	
	15. Cl,	
	16. blood glucose,	
	17. HbA1c,	
	18. serum prolactin	

All laboratory data will be reported in conventional units. Out-of-reference-range values will be flagged as high (H) or low (L) in the listings.

For analysis purposes, values preceded by a “<” sign (i.e. those below the limits of quantification) will be set as missing. If values preceded by a “>” sign (i.e., those above the limits of quantification) are observed, handling will be discussed at BDRM. Note that these values with a “<” or “>” sign will be presented values as reported from the laboratory in the listing.

Mean change from baseline to Week 6 (LOCF) in selected parameters, which are serum prolactin concentration, glucose and HbA1c, will be analyzed using a nonparametric rank ANCOVA. For each pairwise comparison versus placebo, values of the change from baseline at LOCF endpoint and baseline values will be ranked. A linear regression will be conducted on the ranked change from baseline with ranked baseline value as independent variable to produce regression residuals. Using the values of the residuals as scores, Mantel-Haenszel row mean score tests will be produced for each DSP-5423P group versus placebo (Stokes, Davis, & Koch, 1995).

```
* compute the ranks of the response variable and covariate;
proc rank data = &ads out=ranks npuls12 ties=mean;
  var chg base;
  ranks rkchg rkbases;
```

Statistical Analysis Plan

Version: 2

Study No. D4904020

```
run;
* calculate the residuals from the linear regression;
proc glm data=ranks;
  model rkchg=rkbase;

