  output out=residual r=resid;
run;
* CMH mean score statistics are used to compare the groups;
proc freq data=residual;
  tables trt01p*resid / cmh2;
  ods output diffs=diff;
run;
```

Markedly Abnormal Post-Baseline Laboratory Values (MAPLV) for selected laboratory parameters can be found in Table 1. The criterion of MAPLV is satisfied if a value falls into the markedly abnormal range. Subjects will be represented in the count of a particular MAPLV if they have experienced that MAPLV at least once in the post-baseline (including unscheduled visits), regardless of baseline value, up to and including LOCF endpoints and repeat for each country. Only parameters with MAPLV throughout the study period per subject will be listed.

Table 1 Criteria for Markedly Abnormal Post-Baseline Laboratory Values

Hematology Parameter	Markedly Abnormal Range
Hemoglobin	Male: ≤ 11.5 g/dL
	Female: ≤ 9.5 g/dL
Hematocrit	Male: $\leq 37\%$
	Female: $\leq 32\%$
WBC	$\leq 2.8 \times 10^3/uL$
	$\geq 16 \times 10^3/uL$
Platelets	$\leq 75 \times 10^3/uL$
	$\geq 700 \times 10^3/uL$
Chemistry Parameter	Markedly Abnormal Range
ALT	$\geq 3 \times ULN$
AST	$\geq 3 \times ULN$
Alkaline Phosphatase	$\geq 1.5 \times ULN$
Na/Sodium	< 130 mEq/L
	> 150 mEq/L
K/Potassium	< 3 mEq/L
	> 5.5 mEq/L
Cl/Chloride	< 90 mEq/L
	> 115 mEq/L

Statistical Analysis Plan

Version: 2

Study No. D4904020

Blood Glucose (fasting)	< 50 mg/dL > 250 mg/dL
HbA1c	≥ 7.5%
Total Bilirubin	> 2 x ULN
Blood Urea Nitrogen	> 30 mg/dL
Creatinine	> 2.0 mg/dL
CK	> 3 x ULN
Serum Prolactin	≥ 5 x ULN
Triglycerides (fasting)	> 300 mg/dL
Total Cholesterol (fasting)	> 300 mg/dL

Box plot of observed value of the hematology and blood chemistry parameters will be provided for the double-blind treatment phase and the DSP-5423P treatment period by the treatment group and visit.

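### The markedly abnormal laboratory counts in SAP 7.7.5 combine abnormalities present at entry with new ones, and no planned laboratory table separates them

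*SAP*

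**What the plan says.** SAP 7.7.5 defines the measure by absolute limits alone: "The criterion of MAPLV is satisfied if a value falls into the markedly abnormal range". A subject enters the count if this happens "at least once in the post-baseline (including unscheduled visits), regardless of baseline value, up to and including LOCF endpoints". SAP Table 1 sets the HbA1c limit at 7.5% or higher.

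On the entry side, Protocol 8.1.2 excludes "Patients with HbA1c (NGSP) of 8.4% or higher". The listed entry criteria give no numeric limit for prolactin, CK, triglycerides or total cholesterol, which also appear in Table 1.

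On scope, SAP 7.7.5 opens by covering the double-blind phase on the safety population and also laboratory data "for the DSP-5423P treatment period on the DSP-5423P dosed population". The MAPLV paragraph names no period. Its listing rule refers to the whole study: "Only parameters with MAPLV throughout the study period per subject will be listed". The parallel rule for vital signs and weight in SAP 7.7.6 names both periods. SAP 2.2 describes the extension as follows: "Open-label treatment phase: Multicenter, open-label, flexible dose design".

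Other safety displays take account of baseline. SAP 7.7.3 (C-SSRS) gives counts of any ideation or behavior after baseline and also emergence counts, where subjects already positive "at baseline will be excluded from denominator in calculation of percentage". SAP 7.7.7 plans a shift from baseline for ECG interpretation.

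**The concern.** The HbA1c entry limit and the MAPLV limit overlap. Someone can be properly enrolled while already in the range that the safety table calls markedly abnormal, and can then appear in that table with no change on treatment. Protocol 10.3.6 names diabetes among the complications whose treatment is, in principle, continued unchanged, so such subjects are foreseen.

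What is at stake is how the categorical safety tables are read. A reader will want to know how many subjects newly crossed a limit on drug. The planned count answers a different question: how many were ever in range after baseline. In the randomized phase the placebo column gives some calibration. In the DSP-5423P treatment period there is no such column. For subjects who started on placebo, an abnormality that arose on placebo and persists would be counted after the switch to active drug.

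**Working it through.** **1. Overlap of the limits.** Inputs: exclusion at 8.4% or higher (Protocol 8.1.2); MAPLV at 7.5% or higher (SAP Table 1).

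| HbA1c at entry | Eligible | In MAPLV range if unchanged |
|---|---|---|
| 7.4% | yes | no |
| 7.5% | yes | yes |
| 8.0% | yes | yes |
| 8.3% | yes | yes |
| 8.4% | no | (yes) |

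The overlap is 7.5% to below 8.4%, or 7.5-8.3% at one decimal.

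**2. What else in 7.7.5 uses baseline.** Changes from baseline are summarized by visit. A rank ANCOVA against placebo covers prolactin, glucose and HbA1c at Week 6 (LOCF) only. Box plots show observed values by visit. None of these yields a number of subjects who newly crossed a limit. There is no laboratory shift table.

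**3. Size.** The plan states no figure to reproduce. Let p0 be the share entering in range, s the chance that such a subject still has at least one post-baseline value in range, and e the true emergence rate among the rest. The expected counted proportion is

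counted = p0 × s + (1 − p0) × e.

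The documents give none of these, so all values are assumptions. Take e = 1% on placebo and 3% on active, so that a count among subjects not in range at baseline would show a ratio of 3.00.

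Worked case, p0 = 3%:
- s = 1.0: placebo 0.03 + 0.97 × 0.01 = 3.97%; active 0.03 + 0.97 × 0.03 = 5.91%; ratio 1.49; difference 1.94 points.
- s = 0.7: placebo 0.021 + 0.0097 = 3.07%; active 0.021 + 0.0291 = 5.01%; ratio 1.63; difference 1.94 points.

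| p0 | s | Placebo | Active | Ratio | Difference (points) | Share of active count already in range at entry |
|---|---|---|---|---|---|---|
| 1% | 0.7 | 1.69% | 3.67% | 2.17 | 1.98 | 19% |
| 1% | 1.0 | 1.99% | 3.97% | 1.99 | 1.98 | 25% |
| 3% | 0.7 | 3.07% | 5.01% | 1.63 | 1.94 | 42% |
| 3% | 1.0 | 3.97% | 5.91% | 1.49 | 1.94 | 51% |
| 5% | 0.7 | 4.45% | 6.35% | 1.43 | 1.90 | 55% |
| 5% | 1.0 | 5.95% | 7.85% | 1.32 | 1.90 | 64% |

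With 167 per arm (Protocol 15.1), a prevalence of 1-5% means 1.7 to 8.4 subjects per arm in range at entry. The percentages in the table do not depend on arm size.

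**4. A table without a control.** If emergence is only 1% and p0 = 3%, the count shows 3.07-3.97%. The pre-existing share is 0.021/0.0307 = 68% to 0.03/0.0397 = 76%, and nothing in that table would reveal it.

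**The case against.** The strongest reply is that this is a declared choice. The SAP calls the measure post-baseline, says openly that baseline is disregarded, and never labels these values treatment-emergent. No passage contradicts it. Baseline also enters elsewhere: change summaries, the Week 6 rank ANCOVA, listings with high and low flags, and adverse event reporting of clinically significant laboratory findings (Protocol 12.2), summarized by onset date. All of that stands. It makes this a gap in presentation, not an error, and the primary analysis is untouched. But the ANCOVA stops at Week 6 and covers three parameters, the adverse event route depends on the investigator's judgment, and the listings would have to be tallied by hand.

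A reader might infer more than the documents support:

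- *Everyone who enters in range is counted.* No. At least one post-baseline value must be in range; a subject below 7.5% at every post-baseline visit is not counted.
- *The randomized comparison is biased.* No. Entry abnormalities are balanced in expectation, and the absolute difference hardly moves. The ratio is also not something the SAP computes.
- *The C-SSRS section shows that an emergence count should replace the planned one.* No. That section reports both kinds of count. Replacement would also remove from view subjects who start in range and worsen.
- *The open-label use is explicit.* It is inferred from the opening of 7.7.5. For the 40 and 80 mg groups, the DSP-5423P treatment period begins at double-blind Day 1, so it is not purely the open-label phase.
- *QTc has the same gap.* SAP 7.7.7 already has criteria for increases above 30 and 60 msec from baseline.

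**Conclusion.** The point holds as a minor improvement to the safety tables. That the two HbA1c limits overlap, and that no planned laboratory table separates pre-existing from new abnormalities, both follow directly from the text. The size does not: prevalence at entry, persistence and emergence are all assumed. Over 1-5% prevalence and 70-100% persistence, a true ratio of 3 would be displayed as 2.17 down to 1.32, with the difference between arms staying at 1.9 to 2.0 points. In the double-blind phase this is dilution and noise. The consequence is larger in the DSP-5423P treatment period, if the counts are produced there as the section opening implies, because no concurrent placebo column shows how much was present at the start.

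**What to change.** Keep the planned MAPLV count. For each period add one of two displays:

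- a count among subjects not in range at the relevant baseline, with subjects already in range reported separately; or
- a table of baseline status by worst post-baseline status, which shows both groups at once.

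The baselines exist in SAP 6.3. For the double-blind phase, and for the 40 and 80 mg groups throughout, it is "Defined as the last non-missing data of CRF Screening or CRF Day 1 (Baseline) visit on or before Day 1". For placebo-first subjects in the DSP-5423P treatment period it is the on-treatment baseline. Name the periods in the MAPLV paragraph, as 7.7.6 does for vital signs. Showing both counts follows the C-SSRS pattern.

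The cost is one extra table from data already collected. The emergence count has a slightly smaller denominator and says nothing about subjects in range at baseline, which is why the planned count should stay beside it. How far those subjects moved within the range would still be read from the listings.

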7.7.6 Vital Signs and body weight

The following vital signs as well as body weight and BMI will be listed and summarized by treatment group and visit including LOCF endpoints for double blind phase using the safety population and for the DSP-5423P treatment period using the DSP-5423P dosed population. Observed values and change from baseline values will be summarized in descriptive statistics:

- Sitting systolic blood pressure (mmHg);
- Sitting diastolic blood pressure (mmHg);
- pulse rate (beats/min);
- body temperature (°C).

Markedly Abnormal Post-Baseline Vital Signs (MAPVS) are defined in Table 2. Subjects will be represented in the count of a particular MAPVS if they have experienced that MAPVS at least once in the post-baseline (including at unscheduled visits), regardless of baseline value, up to and including LOCF endpoints for the double blinded phase using the safety population and the DSP-5423P treatment period using the DSP-5423P dosed population. The subjects with parameter met MAPVS criterion will be listed.

Table 2: Criteria for Markedly Abnormal Post-Baseline Vital Signs

Parameter	Markedly low	Markedly high
Weight	≥ 7% decrease from Baseline	≥ 7% increase from Baseline

Box plot of observed value of the vital signs and body weight will be provided for the double-blind treatment phase and the DSP-5423P treatment period by the treatment group and visit.

7.7.7 Electrocardiograms

ECG parameters (RR interval, QT interval, PR interval, QRS interval, and QTc interval (QTc Fridericia [QTcF] and QTc Bazett [QTcB]) will be listed and summarized by treatment group and visit including LOCF endpoints for the double-blind treatment phase using the safety population and for the DSP-5423P treatment period using the DSP-5423P dosed population. Observed values and change from baseline values will be summarized.

Similarly, interpretation of ECG (normal, abnormal) will be listed and summarized as frequency and percentage by treatment group and visit including LOCF endpoints. Shift from baseline will be summarized as well. Findings of ECG will be listed. If irregular interpretation is obtained, for example “Not evaluable”, it will be set to missing.

QT prolongations are defined in Table 3. For each criterion, subject with abnormal value at least once in the post-baseline (including unscheduled visits) will be identified for the double-blind treatment phase using the safety population and for the DSP-5423P treatment period for the DSP-5423P dosed population. Frequency and percentage of subjects with QT prolongation for each criterion will be summarized by treatment group.

Table 3: QT Prolongation

Parameter	QTc Prolongation
QTcB, QTcF	> 450 msec
QTcB, QTcF	> 480 msec
QTcB, QTcF	> 500 msec
QTcB, QTcF	> 30 msec increased from baseline
QTcB, QTcF	> 60 msec increased from baseline

7.7.8 Subgroup Analysis

Subgroup analysis will be performed for TEAE and Summary Statistics of DIEPSS total score (excluding overall severity). Subgroup analysis will include sex, age, race (only TEAE), and country and will be done for the double-blind treatment phase using the safety population and for DSP-5423P treatment period for the DSP-5423P dosed

population. Age will be dichotomized as less than 65 years and older than or equal to 65 years.

C-SSRS will also be summarized by country as specified in 7.7.1.

For the double-blind treatment phase, subgroup analyses of before and after the interim analysis will also be performed for adverse events where the before subgroup will consist of the subjects included in the interim analysis (1st to 251st randomized subjects) and the after subgroup consists of the remaining subjects.

7.8 Pharmacokinetic Analysis

Summary statistics of plasma concentrations of blonanserin and M-1, and ratio of plasma concentration of M-1 to blonanserin (ie, M1/blonanserin) will be calculated for the PK population at Week 1, 2, and 6 in the double-blind treatment phase by treatment group and at Open-Week 28 (Week 34) and Open-Week 52 (Week 58) in the open-label treatment phase by the latest dose prior to the PK sampling. Summary statistics will include n, mean, SD, CV%, maximum, median, minimum, geometric mean, and geometric CV%. Treatment groups for the double-blind treatment phase will be 40MG and 80MG group. For the open-label treatment phase, concentrations and ratios will be summarized by the latest dose prior to the PK sampling (ie, 40, 60, or 80 MG).

Data below detection limit will be handled as missing and not be included in summary statistics, but the listing.

Summary statistics of plasma concentration of blonanserin, M1, and their ratio at each dose will also be summarized by subgroup. Subgroups will include sex, age group, application site, race, and country. Age will be dichotomized as less than 65 years (non-elderly) and older than or equal to 65 years (elderly).

Subgroup will further be examined for plasma concentration of blonanserin and M1 at Week 6 in the double-blind treatment phase and at Open-Week 28 (Week 34) in the open-label treatment phase. The ratio of the geometric means and the corresponding 90% confidence intervals will be estimated for the ratios of elderly/non-elderly, female/male, each country/Japan, and each race/Asian. Plasma concentrations will be natural log transformed and analyzed by a linear model, then the estimates for difference between subgroups and their confidential intervals will be back-transformed (ie, using exponential function) to obtain the estimates for the ratio. The model will include treatment (or the latest dose) and subgroup as fixed effects.

```
proc mixed;  
  class dose sex age country race;  
  model ln_pc = dose age sex country race;  
  lsmeans dose age sex country race / diff=control ('40', '0', 'Male',  
'Japan', 'Asian') cl alpha=.10;  
run;
```

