## 4.2 Study Conduct Rationale

In the clinical study in Japanese healthy adults, 1, 2, or 3 patches of DSP-5423P 32 mg/40 cm^2 were applied to 9 patients each for 24 hours. In addition, 2 patches of DSP-5423P 32 mg/40 cm^2 were applied to 9 patients once daily for 10 days. The results showed that the plasma blonanserin concentration increased depending on the number of patches applied and that the steady state was nearly reached after repeated administration for 7 days.

A new patch formulation, DSP-5423P 20 mg/40 cm^2 was prepared. Pharmacokinetics, after the application of a single patch, were compared between these 2 patch formulations. The results showed that a comparable amount of blonanserin absorption was obtained with these 2 patch formulations. Therefore, the new formulation, DSP-5423P 20 mg/40 cm^2 was used in the following studies.

The phase 2 study of DSP-5423P was conducted in patients with schizophrenia to determine the recommended doses for phase 3 studies. Striatal dopamine D2 receptor occupancy and plasma drug concentrations after application of DSP-5423P at doses of 10 to 80 mg/day for 2 weeks were compared with results obtained after administration of DSP-5423 (tablet formulation of blonanserin). The results suggest that DSP-5423P 40 mg/day and 80 mg/day may be comparable to DSP-5423 (tablet) 8 mg/day and 16 mg/day, respectively. Since the clinical efficacy of antipsychotics reportedly correlates with dopamine D2 receptor occupancyref.7, 8, DSP-5423P at doses of 40 and 80 mg/day is expected to demonstrate efficacy corresponding to that of DSP-5423 (tablet) at doses of 8 and 16 mg/day, respectively.

In clinical studies of DSP-5423P in healthy adult volunteers or subjects with schizophrenia, no clinically significant adverse events have been reported at doses up to 80 mg, demonstrating tolerability on the skin of application sites.

The phase 3 confirmatory study is designed to be conducted in a randomized, double-blind, placebo-controlled, parallel-group manner. The primary endpoint will be the change in Positive and Negative Syndrome Scale (PANSS) total score from baseline at Week 6. DSP-5423P will be applied for 6 weeks at doses of 40 and

80 mg/day.

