#### **The guidance for application of the study drugs**

The subjects will be instructed as below:

1. The study drug will be applied directly to normal healthy skin after removing the transparent liner.
2. When the study drug patches are replaced, new patches of the study drug will be applied as soon as possible.
3. The current application site of the study drug will be protected from heat. For instance, the application site should not be warmed with a portable body warmer or hot air from a heater.
4. The current application site of the study drug will be protected from water. Before taking a bath or shower, the study drug should be removed. After taking a bath or shower, new patches of the study drug should be immediately applied to thoroughly dried skin (within approximately 1 hour after removing the previous patches).
5. The locations of previous and current applications of the study drug will be protected from light outdoors by clothing or other appropriate measures from the beginning of the washout phase until the follow-up visit.
6. No other adhesive skin patches are to be overlaid on the current application site of the study drug. No liniments should be used at the current application site of the study drug. The study drug should not be applied to any site where liniments are used.

7. Surgical tape should be used to maintain the study drug at the application site if any patches are detached or are about to become detached. When patches which have detached from the application site cannot be reapplied, no new patches will be applied until the next scheduled application.
8. The used patches will be adequately disposed to prevent anyone else from misusing them.

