### **15.3.7 Pharmacokinetic Analysis**

#### **15.3.7.1 Double-blind treatment phase**

Plasma concentrations of blonanserin and M-1 will be summarized at each visit by treatment group. Plasma concentration ratio of M-1 to blonanserin will be summarized at each visit by treatment group.

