5.6 Pharmacokinetic analysis population (PK population)

The PK population will consist of all subjects who meet all the following:

- Subjects who are randomized and apply DSP-5423P at least once during the study
- Subjects who have at least one plasma concentration of blonanserin after application of DSP-5423P

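### The PK summaries drop on-treatment plasma values below the detection limit but keep detectable samples taken up to 7 days after the last patch.

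*SAP*

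**What the plan says.** SAP 7.8 sets the rule: "Data below detection limit will be handled as missing and not be included in summary statistics, but the listing". The statistics it governs are listed in the same section: "Summary statistics will include n, mean, SD, CV%, maximum, median, minimum, geometric mean, and geometric CV"%. They are produced at Weeks 1, 2 and 6 by treatment group, and at Open-Weeks 28 and 52 by latest dose. The section then models log concentration at Week 6 and Open-Week 28: "The ratio of the geometric means and the corresponding 90% confidence intervals will be estimated for the ratios of elderly/non-elderly, female/male", and likewise for country and race. A value set to missing leaves all of these.

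SAP 6.3 A defines post-baseline data: "Defined as the non-missing data on Day 1 through 7 days after the final application of study drug", apart from the screening and baseline visits. Its mapping table sends a PK sample from a discontinuation visit to the earliest empty analysis visit: Week 1, 2 or 6 for Days 1–11, Week 2 or 6 for Days 12–25, and Week 6 from Day 26.

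PK population entry (SAP 5.6) requires this: "Subjects who have at least one plasma concentration of blonanserin after application of DSP-5423P". It does not say whether a below-limit result qualifies.

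Protocol 15.3.7.1 says only this: "Plasma concentrations of blonanserin and M-1 will be summarized at each visit by treatment group". It has no rule for below-limit values. Neither document gives the assay limit, an expected below-limit rate, a planned count of such values, or a sensitivity analysis.

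**The concern.** A below-limit result is not an absent result. It says that the concentration was low, so it is left-censored. Deleting it removes information from one end of the distribution only.

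The mapping rule adds a second problem. A sample drawn days after the last patch does not describe exposure on the assigned dose, yet if it is detectable it enters the same cell as on-treatment samples. The plan thus filters on the measured value (detectable or not) where it should filter on treatment status (on drug or off).

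What is at stake is the description of exposure by dose and visit, and the age, sex, country and race ratios. Pharmacokinetics is one of the stated secondary objectives (Protocol 5.2). With no count of below-limit values in the tables, a reader of the report would have to rebuild it from listings to judge whether the rule mattered.

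**Working it through.** The plan states no figure to reproduce. The direction follows from the rules; the size needs assumed inputs.

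**Assumptions.** On-treatment concentrations in a cell are lognormal with between-subject CV from 40% to 100%, and a fraction f lies below the limit. Neither input comes from the documents.

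**Geometric mean (GM).** With σ = √ln(1+CV²), z_f the standard normal quantile at f, and λ = φ(z_f)/(1−f):

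observed GM / true GM = exp(σλ)

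- σ = 0.385 at CV 40%, 0.555 at CV 60%, 0.833 at CV 100%.
- λ = 0.0269 at f = 1%, 0.1086 at 5%, 0.195 at 10%.

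| Below limit | CV 40% | CV 60% | CV 100% |
|---|---|---|---|
| 1% | 1.010 | 1.015 | 1.023 |
| 5% | 1.043 | 1.062 | 1.095 |
| 10% | 1.078 | 1.114 | 1.176 |

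For example, CV 100% and f = 5% give exp(0.833 × 0.1086) = 1.095. At f = 0 the factor is 1.

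**Spread.** The observed log-SD is the true one times √(1 + z_f λ − λ²): 0.968 at 1%, 0.900 at 5%, 0.844 at 10%. The reported minimum cannot fall below the limit.

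**Subgroup ratio.** Let both subgroups have the same σ and the same limit, and let the true ratio be g. Then observed ratio = g × exp[σ(λ₁ − λ₀)], where λ₁ and λ₀ are the values for the subgroup and the reference. At CV 60% with 5% below the limit in the reference (λ₀ = 0.1086):

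- g = 0.70: 15.8% of the subgroup is below the limit, λ₁ = 0.2870, observed 0.70 × exp(0.555 × 0.1784) = 0.77.
- g = 1.00: observed 1.00.
- g = 1.25: 2.0% is below the limit, λ₁ = 0.0501, observed 1.25 × exp(−0.555 × 0.0585) = 1.21.

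Differences in either direction shrink toward 1.

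**How the two rules combine.** The plan's rules sort samples into four kinds:

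| Sample | Detectable | Below limit |
|---|---|---|
| On drug | kept | deleted |
| Off drug, within 7 days, mapped to an empty visit | kept | deleted |

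For an on-treatment summary, two of the four cells are wrong. On-drug below-limit samples should contribute, and off-drug detectable ones should not. The second error pulls the geometric mean down, against the first, so the net direction in a cell that contains both is not determined.

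**Where off-drug samples can come from.** Protocol 13.2 asks for discontinuation assessments within 5 days of the last application, and the SAP admits data up to 7 days. Dosing is once daily, so most of either window lies beyond the last dosing interval.

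**The case against.** The strongest reply is that below-limit values may be rare or absent. Protocol 4.2 reports, for the earlier 32 mg patch in healthy adults, that "the steady state was nearly reached after repeated administration for 7 days", and Protocol 7.2.2 describes little change in concentration within 24 hours. Subjects are in hospital until Day 14, which covers the scheduled Week 1 and 2 samples. This stands. If typical levels were 10 times the limit, a lognormal tail would put only 0.0016% of samples below it at CV 60% and 0.28% at CV 100%, with inflation of about 0% and 0.7%. The 5% row in the working implies a geometric mean only about 1.9 to 3.9 times the limit.

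Second, the tables show n, below-limit results stay in the listing, and these outputs carry no hypothesis test. That limits the harm, but n alone does not separate below-limit samples from samples never taken.

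Third, the current rule already removes off-drug samples that are below the limit. True, but it leaves the detectable ones in.

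Fourth, substituting half the limit would be no clear improvement. It adds artificial low values to log concentrations and makes the M-1/blonanserin ratio arbitrary. This also stands, and the fix avoids it.

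A reader might infer that the rule hides precisely the subjects with poor patch wear. The documents do not show that. For a detached patch that cannot be reapplied, "no new patches will be applied until the next scheduled application", but nothing shows that one missed interval brings a value below the limit. Such values can also come from stopped drug or, for M-1, from low metabolite levels. The bias is in the group statistic, not in those subjects. A reader might also infer that subgroup ratios are inflated; under a common limit they move toward 1. Larger inflation can be produced by assuming a near-unexposed subset: 5% of samples at one tenth to one twentieth of the others' geometric mean gives 0.1^(−0.05) = 1.12 to 0.05^(−0.05) = 1.16. That result rests entirely on the assumed level.

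**Conclusion.** The point holds as a matter of rule and direction. SAP 7.8 deletes the lowest on-drug concentrations, SAP 6.3 admits detectable off-drug ones, and nothing in either document offsets this. If on-treatment below-limit values occur, their deletion makes exposure look higher and less variable than it was, and generally makes subgroups look more alike. Subgroups that differ in non-application or in off-drug sampling could depart from that pattern.

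The size cannot be established from the documents. Under the lognormal assumption it is small at about 1% below the limit, material from roughly 5%, and nil if there are none. The efficacy conclusions do not depend on it. The change is still worth making: it is inexpensive, pharmacokinetics is a stated objective, and SAP 7.9 finalises PK population membership after unblinding with PK data in hand, so the entry rule should be fixed beforehand.

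**What to change.** Amend SAP 5.6, 6.3 and 7.8 as follows.

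1. Use the recorded sampling times and the times of the last two applications (Protocol 11.4) to exclude samples taken after the dosing interval of the last application from the on-treatment visit summaries and the ratio models. List or summarise them separately.
2. Report n (%) below the limit for each analyte, dose and visit, and state the assay limit.
3. Estimate geometric means and the ratio confidence intervals with on-treatment below-limit values treated as left-censored in a lognormal likelihood, at least as a sensitivity analysis beside the present exclusion rule. Leave the M-1/blonanserin ratio missing when either analyte is below the limit.
4. State that a below-limit result counts as a plasma concentration for PK population entry.

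The cost is SAP wording, some extra programming and a distributional assumption in the censored model. No new data are needed.
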